## 1.3 Rationale

### 1.3.1 Adolescents Living with HIV/AIDS

Despite improved access to effective ART, AIDS-related deaths among youth have tripled since the year 2000. AIDS is now the number one cause of death among adolescents in Africa and the second leading cause of death among adolescents globally (29). Although evidence indicates that stress and mental health-related symptoms significantly contribute to long-term morbidity, poor ART adherence, (26, 76) and ultimately mortality (77, 78), evidence-based mental health interventions for this highly vulnerable group are woefully lacking (79, 80). Likewise, few, if any programs address caregiver stigma and negative attitudes even though these factors have been shown to play a key role in promoting or impeding mental health and medication adherence for youth living with HIV (81). This study intentionally includes caregivers so as to clarify the role of caregiver attitudes in mitigating mental health distress among adolescents living with HIV.

There have been many efforts to scale up effective ART. Unfortunately, in the absence of providing evidence-based mental health interventions and the lack of resources to deliver effective programs, millions of adolescents living with HIV in low-income countries will remain disproportionately vulnerable to accelerated disease progression. The need for effective mental health interventions for youth living with HIV, especially those that can be administered by carefully trained non-professionals in low-resource settings, is a public health emergency. The COVID-19 pandemic has both revealed and exacerbated gaping holes in the health system to serve priority populations and the high rates of mental distress has surfaced as a major consequence. This study addresses these gaps by testing the effects of TI-CBT enhanced to address effects of depression, anxiety, and trauma symptoms on ART adherence among 15-19 year-olds living with HIV in low-resource settings. Further, by training young adult peers living with HIV to deliver the

intervention, the study can build in-country capacity for mental health care. As a secondary outcome, the impact of the intervention on ART adherence will be evaluated.

### 1.3.2 Adolescents and HIV- Scientific Advancements

This study offers a number of potential contributions to the science related to adolescents and HIV, which include: improvement of mental health distress as an outcome measure; focus on high-risk under-represented priority population; peer-delivery of the intervention; the role of inflammatory biomarkers in mental health distress symptoms; and strategies to systemize the adaptation of the intervention for new populations.

*Mental Health Distress:* First, there are currently no published evidence-based interventions that have a primary outcome to improve mental health among adolescents living with HIV who are 15 to 19 years old in sub-Saharan Africa (76). Many African countries lack adequate mental health resources to provide effective programs. No published studies included youth specifically based on mental health criteria or were powered to evaluate the impact of the intervention on mental health. Finally, no interventions have been tailored to 15 – 19 year-olds specifically, even though this age group constitutes the vast majority of adolescents living with HIV in sub-Saharan Africa.

*Priority Population:* Second, the 15-19 year-old age group represents a high-risk yet underrepresented population in research. Several reasons support a focus on 15-19 year-olds and their mental health. One, mental health problems typically first emerge during adolescence (82), and intervening during this early life stage may prevent a long-term trajectory of poor mental health. Two, during adolescence, adherence to ART is tenuous at best (77). Without intervention, there is a risk of developing HIV resistant mutations, virologic failure, and a greater likelihood of HIV transmission to others (83). Three, adolescent (vs. adult) behavior is more malleable and responsive to change. New behaviors (e.g., adherence) are more likely to be adopted and maintained if they are established at a younger age. Changing health behavior during adolescence is easier than changing behavior in adulthood after habits are formed and entrenched. Four, along with adolescence, comes the beginning of sexual activity and “romantic” involvement. This is an important opportunity to challenge traditional gender roles and power dynamics, including preventing intimate partner violence. The intervention will address local gender norms and stereotypes in the context of sexual relationships, the importance of safer sex and delayed sexual debut, and the role of ART adherence in preventing HIV transmission. Finally, 15-19 year-olds are still connected to and reliant on their families and caregivers for support and care. By leveraging caregivers as collaborators in the intervention, adolescents will likely adopt positive behavior changes. Taken together, this study addresses these important factors and represents innovation over existing published interventions.

*Peer-delivered:* A third area where this study represents an advancement to the science is the use of young adult peers living with HIV to deliver the intervention to their younger peers. This innovation is based on a robust literature demonstrating that peers can be trained to deliver adolescent health promotion programs (84), including school-based sexual health interventions (85-87). Still, rigorous outcome research on peer-led interventions for adolescents has been mixed and this study offers an opportunity to inform the research (88). For example, some studies found positive effects of peer-led interventions with regard to HIV/AIDS knowledge (86-89), attitudes, beliefs, and intentions about risky sex and condom use (86, 90, 91), self-efficacy to refuse sex, and delay sexual behaviors (92), condom use (93), and general health behaviors (94). However, other published papers report no impact on youth’s risk reduction intentions, (95) sexual behavior (90, 96), condom use (95), or acquisition of sexually transmitted infections (86, 88). The contradictory findings are attributable in large part to an absence of methodological rigor, lack of equivalent

comparison groups, inadequate sample details, no pre-intervention data, and weak study designs (49, 88, 90, 97-107). In fact, a comprehensive meta-analysis of adolescent peer-led health promotion programs revealed that only 12 out of 210 studies were deemed methodologically sound (e.g., had an explicit theoretical framework, clear sample and methodology, stated aims and objectives) (49). Ten of the 12 were judged effective for one or more behavioral outcomes or non-behavioral outcome (knowledge, beliefs, and attitudes). The poor methodological state of the field has led to numerous calls for more rigorous evaluations of peer-led programs (49, 52, 104), which this study will provide.

*Inflammatory Biomarkers.* Fourth, the role of inflammation in mental health symptoms, including depression, anxiety, and post-traumatic stress, is increasingly recognized (105-107), yet poorly understood. In both individuals with and without HIV, elevated levels of high-sensitivity C-reactive protein (hsCRP), interferon  $\alpha$  (IFN $\alpha$ ), fibrinogen, sP-selectin, and interleukin 6 (IL6) have been associated with the development of depression and other neurocognitive disorders. Furthermore, in individuals living with HIV, inflammation, measured by soluble cluster of differentiation 14 (sCD14), interleukin 1 $\beta$  (IL1 $\beta$ ), IL6, D-dimer, tissue necrosis factor  $\alpha$  (TNF $\alpha$ ), chemokine C-C motif ligand 10 (CCL10), and vascular cell adhesion molecule 1 (VCAM1) in the blood compartment and at mucosal sites has been shown to be a major component of HIV pathogenesis (108-113). Thus, inflammation due to HIV and mental health symptoms such as depression may synergize in individuals with HIV, further increasing morbidity. Because inflammation may respond to interventions that improve adherence to and effectiveness of antiretroviral treatments, this study may offer some clues into these processes.

Relatedly, studies with non-HIV infected individuals and animal experiments suggest that mental health and behavioral outcomes are associated with markers of inflammation. For example, depressive symptoms such as fatigue, cognitive impairment, decreased social interaction and exploration, and loss of appetite may in part derive from chronic immune dysregulation and related cytokine activity (114). In two clinical trials, the level of C-reactive protein (CRP) in peripheral blood at pre-treatment baseline differentially predicted treatment responses to the antidepressants citalopram and nortriptyline (115), as well as treatment response to antidepressant augmentation with the TNF- $\alpha$  inhibitor infliximab (116). These findings suggest that a subset of depressive syndromes might be driven by inflammatory mechanisms. In healthy adult women, post-traumatic stress disorder (PTSD) due to childhood sexual abuse is associated with a significantly higher mean percentage of CD8+ T-cells expressing early activation marker CD45RA+; furthermore, the PTSD symptom severity is positively associated with the CD45RA+% (117). In vitro data suggest that an association between PTSD or trauma and immune outcomes may be driven by neuroendocrine and neuroimmune mechanisms. Dexamethasone (DEX)-induced inhibition of T-cell proliferation was significantly lower in cell cultures obtained from veterans with PTSD compared to veterans without PTSD and healthy controls. DEX-induced increase in LPS-stimulated IL-10 was less pronounced in traumatized veterans with and without PTSD compared to healthy controls. These results suggest that trauma exposure can induce changes in glucocorticoid receptor binding characteristics, while PTSD also induces resistance of T-cell proliferation to DEX (118).

Immune and inflammatory markers have been associated with certain psychological and behavioral outcomes in at least four studies of individuals living with HIV. In one IMPAACT-based study, CD4 nadir  $< 25\%$  was associated with increased risk of incident depression in children with PHIV (119). In a US cohort of pregnant and postpartum HIV+ women, the risk of perinatal depression was independently associated with CD4+ nadir  $\leq 200$  cells/mL (105). In a cohort of low-income, urban African American adults with HIV, untreated depression was associated with current CD4 T cell counts  $< 350$  cells/mL, while depression treated with

antidepressants or absence of depression were not associated with CD4 count, even after controlling for the mediating effect of non-adherence to ART (106). In a US-based cohort of 114 viremic HIV+ adults, a positive screen for PTSD was associated with significantly higher total WBC count, total granulocytes, CD8%, and memory CD8%; lower naïve CD8%; and increased likelihood of having a hsCRP level >3 mg/L (107).

Studies of adults living with HIV and adherent to ART showed the majority of adverse clinical outcomes with high morbidity and mortality were non-AIDS related (i.e., diabetes mellitus, non-AIDS malignancies, or severe cardiovascular, vascular or liver disease) (120-123). In the current treatment era, increased plasma inflammatory biomarkers appear to be valuable predictors of non-AIDS-related morbidity and mortality among adults living with HIV (20, 124, 125). Taken together, monitoring and exploring the impact of inflammatory biomarkers as part of this study will provide important scientific information regarding the effect of a neurobehavioral intervention on plasma inflammatory biomarkers in this age group.

*Adaptation of Intervention for New Populations.* Finally, this study will provide much needed guidance on the most effective strategies to systemize the adaptation process of evidence-based programs to low-income settings and diverse cultural contexts (126). Although the ADAPT-ITT model has been used previously, this study will allow for careful documentation of key adaptation strategies that should be used to tailor the intervention to new contexts, including methods for translation and back translation. In moving forward, these procedures can be used as the intervention is taken to scale.

### 1.3.3 Rationale for Scale-up of Intervention and Study Design

This study will employ the intervention developed in Rwanda (i.e., KIP) to evaluate replication, scale-up, and feasibility to other LMICs that lack the strong mental health resources available in Rwanda. Rwanda is a unique region in sub-Saharan Africa because of its availability of trained psychologists and wrap-around resources for adolescents and young adults living with HIV. Hence, it is unclear if KIP's study model will work in more resource-constrained settings.

Unlike previous research, this study will screen and enroll youth who meet pre-defined criteria on one or more of three well-validated mental health measures of depression, anxiety and/or trauma. This scientific advancement has two important implications. First, no single site is likely to have a sufficient number of youth who qualify with mental health problems to conduct a rigorous 2-arm randomized controlled trial. Hence, to adequately test intervention effects with sufficient methodological rigor, access to the multiple sites within the IMPAACT network is essential. Second, because previous research included all interested youth living with HIV (i.e., *KIP* and *Sauti ya Vijana*), findings may have potentially obscured treatment effects for those who need it the most. Research indicates that screening youth using locally-validated mental health measures is feasible and has been done in other sub-Saharan African settings. In Tanzania, for example, 25% to 45% of youth reported mental health difficulties that met criteria for significant distress (4, 127). Two studies in South Africa revealed similar rates of mental health problems as Tanzania; among school-going youth in Gauteng Province, South Africa, 23% reported depression, 27% endorsed suicidal ideation in the last month, and 22% indicated lifetime suicide attempts (128). Similarly, among youth living with HIV in Soweto, South Africa, 20% met criteria for depression (major depressive disorder, minor depression, and dysthymia), 22% reported post-traumatic stress disorder, and 42% indicated suicidal ideation in the past two weeks (129). Testing the intervention with youth who report clinical levels of mental health symptoms will provide a more robust evaluation of intervention efficacy.

In addition to mental health, this study will evaluate the intervention's impact on ART adherence using well-validated biomedical outcomes (e.g., quantitative ART drug concentration levels from hair samples and viral loads that are systematically timed with follow-up evaluations (130-133). Prior research relied on self-reported adherence or viral load and CD4 data derived from medical records and not timed to study assessments (e.g., KIP). These approaches have significant limitations in time matching and quality. Hair collection is non-invasive and has no special storage requirements. Data from hair demonstrated associations with ART adherence and drug exposure among children, adolescents, and adults (133-135). With these biologic markers of adherence and HIV outcomes, the study will be able to systematically link changes in adherence and virologic outcomes to changes in mental health symptoms and the impact of the intervention.

Engaging multiple sub-Saharan sites with minimal (if any) mental health resources will permit a strong and much-needed evaluation of a mental health evaluation delivered by peers and will also increase the generalizability of the findings. Implementation of the study in countries with high volumes of youth 15-19 years of age living with HIV and minimal mental health care infrastructure will enable the largest potential intervention impact while delivering the program in areas of greatest need. Moreover, by tailoring the intervention to several sites, potential for scale-up across countries can also be evaluated.

This study has the potential to impact clinical mental health services for youth living with HIV. If peers can be trained to deliver this mental health intervention and it is effective at reducing mental health distress, this study will provide data for policy and implementation in the future. These data will support sustainability within the study clinics and point to strategies to expand available mental health interventions in other resource-poor settings. This study will offer proof of concept for training non-professional youth leaders to deliver evidence-based interventions and may encourage other clinical settings to implement care that addresses both psychosocial and medical needs of youth living with HIV.

In summary, IMPAACT 2016 will build on prior research findings and contribute important new knowledge about the effectiveness of TI-CBT on adolescents living with HIV. The study's distinguishing characteristics include: enrolling those youth who screen for mental health distress on at least one of three well-validated mental health measures; being adequately powered to demonstrate change in distress as a result of the intervention; extensive community buy-in and support following engagement through focus groups and advisory board meetings; carefully designed study implementation materials that improve upon those used in previous studies (e.g., training and intervention manuals; tracking spreadsheets; measurement tools); biological measures of ART adherence; greater intervention clarity and reproducibility for the future; increased generalizability and more realistic comparison groups reflecting the typical standard of care in low-resource settings; and a rigorous training protocol for peer leaders that includes a multidisciplinary team (mental health, infectious disease, HIV). Lastly, IMPAACT 2016 is defined to clarify the mechanisms associated with change to allow for even greater intervention precision in the future.

## **1.4 Hypothesis**

The TI-CBT Intervention will result in reduced symptoms of depression, anxiety, and/or traumatic stress compared to the Discussion Control at six months.

## **2 OBJECTIVES**

### **2.1 Primary Objective**

The primary objective of this study is to:

- 2.1.1 Evaluate whether a TI-CBT Intervention is associated with improved depression, anxiety, and/or traumatic stress symptoms for youth living with HIV compared to a Discussion Control at six months.

### **2.2 Secondary Objectives**

The secondary objectives of this study are to:

- 2.2.1 Determine the feasibility, acceptability, and fidelity of a TI-CBT intervention.
- 2.2.2 Evaluate whether a TI-CBT Intervention is associated with improved depression, anxiety, and/or traumatic stress symptoms for youth living with HIV compared to a Discussion Control following the last group session and at 12 months.
- 2.2.3 Assess whether a TI-CBT Intervention is associated with improved ART adherence (hair samples, self-report) and viral suppression (HIV RNA plasma) for youth living with HIV compared to a Discussion Control following the last group session and at six and 12 months.
- 2.2.4 Assess whether a TI-CBT Intervention is associated with improved structural factors for youth living with HIV (HIV stigma and support for adherence; barriers to adherence; gender-based violence; gender roles) compared to a Discussion Control following the last group session and at six and 12 months.
- 2.2.5 Assess whether a TI-CBT Intervention is associated with improved structural factors for caregivers (HIV knowledge, stigma, and support for adherence; barriers to adherence) compared to a Discussion Control following the last group session and at six and 12 months.
- 2.2.6 Assess whether a TI-CBT Intervention is associated with improved behavioral risk outcomes for youth living with HIV (alcohol/drug use; sex-risk behaviors; caregiver report of youth behavior) compared to a Discussion Control following the last group session and at six and 12 months.
- 2.2.7 Identify the individual, social, and structural barriers, and facilitators to implementation of a TI-CBT Intervention.
- 2.2.8 Compare the rates of all targeted adverse events between a TI-CBT Intervention and a Discussion Control for youth living with HIV.

## 2.3 Other Objectives

The other objectives of this study are to:

- 2.3.1 Evaluate whether a booster session at six months is associated with continued improvements in depression, anxiety and traumatic stress symptoms at 12 months.
- 2.3.2 Assess whether youth and caregiver demographic and structural factors moderate the efficacy of a TI-CBT Intervention compared to the Discussion Control.

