## IMPAACT 2016

### Evaluating a Group-Based Intervention to Improve Mental Health and ART Adherence Among Youth Living with HIV in Low Resource Settings

#### SCHEMA

- Purpose:** To evaluate whether an Indigenous Leader Outreach Model (ILOM) of trauma-informed cognitive behavioral therapy (TI-CBT) [referred to as TI-CBT delivered by Indigenous Youth Leaders (IYL)] is associated with improved mental health outcomes and antiretroviral therapy (ART) adherence among youth living with HIV.
- Design:** Multi-site, two-arm, individually randomized controlled trial preceded by Focus Groups and Pilot Testing to adapt the intervention to the local context.
- Study Population:** 15-19 year old youth living with HIV and mental health distress, and their caregivers (if available and agreed to by youth participant).
- Sample Size:** Approximately 192 - 256 youth participants (96 - 128 per arm), plus their caregivers, in the Randomized Trial. Each arm will have 12 - 16 groups with an average of eight youth participants per group (range 6 – 10). Youth participants' caregivers will be assigned to the same arm as their youth participants.
- Prior to the Randomized Trial, Focus Groups comprised of 5-8 youth participants and 5-8 caregivers will be conducted at selected sites. All sites will also conduct a Pilot Test with up to eight youth participants and up to eight caregivers.
- Study Intervention:** In the Randomized Trial, youth participants will be randomized in a 1:1 ratio with their caregivers to one of two study arms as shown below.

Randomized Trial Arms	Youth Participants	Caregivers of Youth Participants
TI-CBT Intervention Arm	Six 2-hour TI-CBT group sessions led by IYL during Weeks 1 to 6 and One 2-hour booster TI-CBT group session at 6 months	Two 2-hour group sessions led by adult study staff during Weeks 1 to 6 and One 2-hour booster group session at 6 months
Discussion Control Arm	Six 2-hour discussion group sessions led by IYL during Weeks 1 to 6 and One 2-hour booster discussion group session at 6 months	Two 2-hour discussion group sessions led by adult study staff during Weeks 1 to 6 and One 2-hour booster discussion group session at 6 months

**Study Duration:** Approximately 22 months total.

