### **3.2 Randomized Trial**

In the Randomized Trial, youth will be individually randomized to either the TI-CBT Intervention Arm or the Discussion Control Arm. Participants will meet as a group within their randomized arm and receive multiple group sessions within an eight-week period as described in [Section 5](#). Each group will include an average of eight youth for an approximate total of 192-256 youth in the Randomized Trial (96-128 youth per arm). TI-CBT and Discussion Control groups in each arm will be mixed-gender unless it is determined necessary to have single-gender groups during the focus group. Mixed gender groups will be required to have a minimum of two participants of each gender.

Each youth group session may be conducted on separate days or an equivalent approach may be implemented in that multiple group sessions may be combined (e.g., group sessions 1 and 2 may be conducted during the same day) based on the Pilot Test and feedback during the adaptation stage (refer to [Section 3.1](#)). IYL’s will facilitate the TI-CBT and Discussion Control group sessions; however, the IYLs delivering the TI-CBT group sessions will be trained in TI-CBT (refer to [Section 5.2](#)), and supervision of IYL will be conducted using the Cascading Supervision Model (refer to [Section 5.3](#)).

Caregivers (as available and with youth permission) will be assigned to the same study arm as their youth. Caregivers will meet as a group for two caregiver-specific sessions on two separate weeks and separate from their youth group sessions. Adult study staff will facilitate the TI-CBT and Discussion Control group sessions; however, the adult study staff delivering the TI-CBT group sessions will be trained in TI-CBT-related content (refer to [Section 5.2](#)).

Youth and caregivers will also receive one two-hour booster group session consistent with their assigned study arm immediately after the six-month evaluations. The booster sessions are meant to enhance treatment effect sustainability (refer to [Section 5.1](#) for additional detail).

Youth and caregivers will complete a follow-up visit immediately after their last group session and two additional follow-up visits at six and 12 months (Refer to [Sections 6.3.5, 6.3.6, 6.3.8, 6.4.3, 6.4.4, and 6.4.6](#)). At these visits, the following will be evaluated:

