- Youth: targeted medical history, focused on mental health; self-reported ART adherence; plasma HIV-1 RNA; ARV concentrations in hair; HIV stigma; barriers to adherence; behavioral risks; gender roles; gender violence; and perception of caregiver behavior.
- Caregivers: HIV stigma, HIV attitudes, HIV knowledge, barriers to adherence, and perception of youth behavior.

Once all participants have completed their six-month evaluations, data from these evaluations will be analyzed to determine the short-term effects of the intervention. Additional analyses to assess the longer-term effects of the intervention, including the effects of the booster group session, will be performed after the completion of follow-up.

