## Youth Participants

**Discussion Control group sessions:** Youth randomized to the Discussion Control Arm will receive the same number and timing of group sessions as the TI-CBT Intervention Arm (Refer to [Section 5.1.1](#)). Each session will be led by IYL who will receive training on running Discussion Control groups (refer to [Section 5.2](#) for detailed information on the IYL training). Discussion topics will be selected by youth in the group. Discussion Control group session will take place at a separate time from TI-CBT youth group sessions in attempt to minimize contamination.

**Booster session:** A booster group session will be conducted following the six-month evaluation on the same day or within one month. This session will consist of one 2-hour open discussion of a topic chosen by the youth participants.

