## 9.3 Randomization

Youth participants in the Randomized Trial will be individually randomized to the TI-CBT Intervention or Discussion Control Arm. If there are youth of the same household (household members) who are both eligible, they will be randomized to the same study arm to avoid contamination. For the purpose of the study, a household member is defined as a person (e.g., sibling) who currently lives in the same dwelling unit and/or shares the same housekeeping arrangements (e.g. performs activities of daily living together). Caregivers will be assigned to the same arm as their youth's randomization. Randomization will be 1:1, using a dynamic permuted block system with balancing by site. Randomization will be stratified by gender to assure approximate balance between study arms.

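### The booster's separate effect, which Objective 2.3.1 and Protocol Section 3.2 set out to assess, cannot be isolated because every youth in both arms is assigned a booster

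*Protocol*

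**What the plan says.** Protocol Section 2.3, Objective 2.3.1 (repeated in the Schema), reads: "Evaluate whether a booster session at six months is associated with continued improvements in depression, anxiety and traumatic stress symptoms at 12 months". It names no comparator. The end of Protocol Section 3.2 schedules, once follow-up is complete, "Additional analyses to assess the longer-term effects of the intervention, including the effects of the booster group session".

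On allocation, Section 3.2 says that "youth will be individually randomized to either the TI-CBT Intervention Arm or the Discussion Control Arm", and Section 9.3 adds: "Randomization will be 1:1, using a dynamic permuted block system with balancing by site". No second randomisation is described.

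On who gets a booster, Section 3.2 says: "Youth and caregivers will also receive one two-hour booster group session consistent with their assigned study arm immediately after the six-month evaluations". The Schema lists "One 2-hour booster TI-CBT group session at 6 months" for the TI-CBT arm and "One 2-hour booster discussion group session at 6 months" for the control arm. For the control youth, Section 5.1.2 describes the content: "This session will consist of one 2-hour open discussion of a topic chosen by the youth participants". SAP Section 2.1 agrees that everyone has a booster after the six-month assessment.

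On analysis, Protocol Table 4 places the outcome for 2.3.1 (numbered 9.2.3.1) in the same row as the 12-month part of secondary Objective 2.2.2. Section 9.5.2 says that other outcomes are analysed much as the primary ones, that is, between arms at group level. SAP Section 1.1 defers these outcomes to a separate SAP, which is not among the documents.

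**The concern.** To say what a booster adds, one needs youth who had the same first six sessions and no booster. The design has none. Under the plan as written, either Objective 2.3.1 repeats the 12-month arm comparison of Objective 2.2.2 under another name, or a contrast between two whole packages is reported as an effect of one session. The second outcome matters to anyone deciding whether the booster is worth delivering when the programme is scaled up. A 12-month advantage for TI-CBT could come entirely from the first six sessions, and a null result could hide a booster that offset decay.

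**Working it through.** The documents give no sample size, power or effect size for Objective 2.3.1, so there is no figure to reproduce. The check is whether the booster effect can be identified.

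**Inputs.** There are two arms (Protocol 3.2 and 9.3). Outcomes are measured at 6 and 12 months (6.3.6 and 6.3.8). The booster comes after the six-month evaluation in both arms (5.1.1, 5.1.2 and 6.3.7). So booster exposure is 0 for everyone at 6 months and 1 for everyone, as assigned, at 12 months.

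**Model for the mean symptom score**, with six terms:

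- μ: control mean at 6 months
- α: arm difference at 6 months
- τ: change from 6 to 12 months common to both arms, such as natural recovery
- δ: persistence or decay of the six TI-CBT sessions relative to control
- β: effect of having any booster
- γ: extra effect of TI-CBT content in the booster

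| Arm | 6 months | 12 months | Change |
|---|---|---|---|
| Discussion Control | μ | μ + τ + β | τ + β |
| TI-CBT | μ + α | μ + α + τ + δ + β + γ | τ + β + δ + γ |

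**What the contrasts estimate.**

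- Between arms at 12 months: α + δ + γ.
- Between arms in change from 6 to 12 months: (τ + β + δ + γ) − (τ + β) = δ + γ.
- Within the TI-CBT arm, before-after: τ + β + δ + γ.

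β never appears without τ, or it cancels. γ never appears without δ. The four cell means identify μ, α, τ + β and δ + γ, and nothing more. In matrix terms, the any-booster column equals the time column and the TI-CBT-booster column equals arm × time, so the rank is 4 for 6 parameters. More participants make the sums more precise but do not separate them. For example, if δ + γ is zero, the data fit equally well with no decay and no booster effect, or with decay of d cancelled by a booster benefit of d, for any d.

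As a check on the reasoning, suppose a 12-month cell without a booster existed in each arm. Its means would be μ + τ (control) and μ + α + τ + δ (TI-CBT). The matrix then has rank 6 of 6 and both booster terms become estimable. The missing comparator is the whole of the problem.

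**Attendance as a substitute.** Booster attendance is tabulated (SAP 5.2.4) and is the only variation in exposure. It is not randomised. It may also be imprecise. The documents give no expected attendance, so the range below is assumed. Take 96 to 128 youth in the TI-CBT arm and 10% loss in each of two half-year intervals (the rate in Protocol 9.3.1), and ignore clustering. Evaluable youth are then 96 × 0.9 × 0.9 = 77.8 to 128 × 0.9 × 0.9 = 103.7. With 80% power and two-sided 0.05, the detectable difference is (1.96 + 0.84) × √(1/n₁ + 1/n₀) SD, where n₁ attend and n₀ do not:

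| Assumed attendance | 96 in arm | 128 in arm |
|---|---|---|
| 95% | 1.46 (73.9 v 3.9) | 1.26 (98.5 v 5.2) |
| 80% | 0.79 (62.2 v 15.6) | 0.69 (82.9 v 20.7) |
| 50% | 0.64 (38.9 v 38.9) | 0.55 (51.8 v 51.8) |

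Clustering would generally widen these figures. Self-selection would bias the comparison whatever the attendance.

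**The case against.** Four points can fairly be made for the plan.

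First, the objective speaks only of association, and outcomes at both visits and attendance are recorded, so something can be reported. This stands in part. A reader might infer that 2.3.1 cannot be answered at all, and that goes too far, because a descriptive answer is available. But the primary objective uses the same verb for a randomised comparison, so the verb does not mark 2.3.1 as descriptive, and Section 3.2 speaks of effects.

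Second, Table 4 and Section 9.5.2 already imply a between-arm comparison. This stands. A reader might infer that only before-after and attendance contrasts remain, or that natural recovery will be credited to the booster. The documents do not support either. They plan no within-arm analysis, and a change shared by the arms (τ above) cancels between them. The fall in symptoms in both arms of the Rwandan predecessor trial (Protocol 1.2.1) is a reason not to read within-arm change as a booster effect, but not evidence that the sponsor intends to. That trial also did not select for distress and had an unusually strong control. What the arm comparison does not remove is the mixing of δ with γ.

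Third, the sentence in Section 3.2 can be read as meaning the package including its booster. That reading is possible, but beside 2.3.1, which singles out the booster, it is not the natural one.

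Fourth, the separate SAP may already carry the right caveat. It may, and we cannot see it. It cannot supply a comparator that the design lacks, and the protocol objective would still need to match it.

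**Conclusion.** Objective 2.3.1 and the matching sentence in Section 3.2 are wrong as written. The booster's separate effect is not identifiable, since only four of six quantities are estimable and no youth is assigned to go without. This rests only on the assignment described in the protocol and SAP. The detectable differences for attendance are illustrations under assumed attendance.

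The reach is limited. The arm contrasts at 12 months and in change from 6 to 12 months remain valid comparisons of packages. The objective ranks below the primary and secondary ones, and the booster follows the six-month evaluation, so the primary analysis, its sample size and the primary report are unaffected. The gain from correcting it lies in what the trial may claim about the booster.

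**What to change.** Reword Objective 2.3.1, its copy in the Schema and the Section 3.2 sentence along these lines: *compare the change in depression, anxiety and traumatic stress symptoms from 6 to 12 months between TI-CBT with its booster and Discussion Control with its booster, as a question of durability.* Change is the part to specify, because the level at 12 months is already covered by Objective 2.2.2. The two should be read together, since the arms may already differ at six months.

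Add two statements there and in the separate SAP for other outcomes: no separate booster effect is estimated, and any within-arm or booster-attendance comparison is descriptive only.

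The cost is a few lines of text. Delivery, visits, randomisation and sample size do not change. The trial gives up a claim that its design cannot support, and 2.3.1 gains content of its own.
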